### Enrollment/Stratification/Randomization/Blinding Procedures

This is a randomized open label observational study. Each subject will be randomized to one of 6 possible dosing regimens shown in the table below (Table 1). For each study period, block randomization will be used to ensure that Dosing Groups are balanced across enrollment time. The randomization will be programmed using R software (<http://cran.r-project.org/> , The R Foundation for Statistical Computing).

Table 1: All possible randomization scenarios

Dosing group	1	2	3	4	5	6
Period 1	33	33	67	67	100	100
Period 2	67	100	33	100	33	67
N (36 total)	6	6	6	6	6	6

### Participant Enrollment Follow-Up

Enrollment will be discussed at PSRT meetings every 6 months.

### Planned Interim Analyses and Stopping Guidelines

Because the study is non-therapeutic and relatively small (N<100) the study team will monitor for safety as described above, but not efficacy.

Assays will be performed real time for the first 6 participants to evaluate if the half-life of TFV-DP in RBC is similar for TAF vs TDF. An analysis will be conducted at week 6 or 8 to assess TFV-DP by fitting the following equation:  $C_t = C_{ss} * (1 - e^{-k * t})$ , where  $C_t$  is TFV-DP in DBS at time  $t$ ,  $C_{ss}$  is the fitted steady state concentration,  $k$  is the fitted first-order elimination rate constant. Note the dose is not required for this equation. For comparison, we will run simulations of TFV-DP in DBS during TDF therapy using data from our ongoing DOT-DBS study (COMIRB 13-0427). If TFV-DP kinetics are similar for TAF and TDF, we would expect the fitted  $k$  to be similar between DOT-DBS and the present study. This interim analysis will only detect very large differences. We will meet as a study team (PSRT and [name]) to assess comparability, and will make decisions about potential study design alterations at this meeting. If study alterations are deemed to be needed, they will be submitted to the IRB prior to implementation.

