## PROTOCOL

- Full Title:** The Cellular Pharmacology of F-TAF in dried blood spots
- Short Title:** TAF-DBS
- Clinical Phase:** I-II
- IND Sponsor:** Exempt
- Principal Investigator:** [name].
- Sample Size:** Approximately 36 who complete the study timeline. IRB approvals will be sought for 72 subjects to allow for screen failures and drop outs.
- Study population:** HIV-uninfected adult participants at low risk for HIV infection. All participants must have a creatinine clearance >60 ml/min (MDRD equation) and no contraindicated medical conditions or medications.
- Participating sites:** The University of Colorado Anschutz Medical Campus.
- Study Design:** Approximately 36 HIV negative subjects will be enrolled. Enrollment will target approximately half women and one third African-Americans or Latino. However, strict quotas will not be imposed. Enrollment will proceed without the need to meet specific race/gender targets. Participants will be randomized to one of 6 sequences consisting of two directly observed dosing regimens, 33%/67%, 33%/100%, 67%/33%, 67%/100%, 100%/33%, and 100%/67%, expressed as % of daily dosing. Each dose regimen will have a duration of approximately 12 weeks. DBS/blood will be collected every week and hair will be collected at 3 week intervals. There will be a 12 week washout period between dose regimens. Additional samples will be collected during this washout period to determine elimination kinetics in hair and DBS/blood.
- The 33% and 67% dosing regimens will skip doses spaced by days (i.e. 67% is two daily doses followed by skipping a day, repeated for 12 weeks; 33% dosing is a daily dose followed by two skipped days, repeated for 12 weeks).
- Study Duration:** For participants, the study lasts for approximately 36 weeks. Recruitment and enrollment will continue for approximately one year, the total study duration is approximately two years.
- Study Regimen:** Volunteers will receive 200mg and 25mg of emtricitabine and tenofovir alafenamide fumarate (F-TAF) according to the regimens outlined above. This medication will be donated by Gilead Sciences, and managed by the University of Colorado Hospital Investigational Pharmacy.

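### The interim build-up equation ignores dose timing, so participants with the same true k get different fitted values on skip-day and daily regimens (minor)

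*Combined protocol and SAP*

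**What the plan says.** The section on planned interim analyses gives the check in outline: "Assays will be performed real time for the first 6 participants", and "An analysis will be conducted at week 6 or 8 to assess TFV-DP". The model is Ct = Css × (1 − e^(−kt)), with Css and k both fitted, and the text remarks: "Note the dose is not required for this equation". The fitted k is then set beside simulations of TDF therapy based on the DOT-DBS study. No numerical limit for similarity is given. The section warns that nothing short of a very large difference would show, and it leaves the judgement and any design change to a study-team meeting.

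The study design paragraph of the protocol describes the two reduced regimens as schedules, not as smaller daily doses: "67% is two daily doses followed by skipping a day, repeated for 12 weeks" and "33% dosing is a daily dose followed by two skipped days, repeated for 12 weeks". Sampling is weekly: "DBS/blood will be collected every week". On allocation, the plan says "Each subject will be randomized to one of 6 possible dosing regimens shown in the table below", and "block randomization will be used to ensure that Dosing Groups are balanced across enrollment time". In Table 1, two sequences begin on 33%, two on 67% and two on 100%.

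**The concern.** The interim curve describes input at an even rate, and daily dosing sampled pre-dose fits it exactly. Two of the three period-1 regimens do not have even input. A 7-day visit interval against a 3-day dosing cycle also means that each weekly sample falls at a different point of the cycle. The plan does not say that the fit, or the TDF simulation it is compared with, takes the dosing pattern into account.

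This is the only in-trial check on kinetics that the documents show, and it may lead to design changes. The half-life matters to the design because the primary dose-proportionality analysis uses week-12 levels from two periods separated by a 12-week washout. With a half-life of 28 days, for example, 84 days is three half-lives: levels reach 87.5% of steady state by week 12, and 12.5% of the period-1 level remains after washout. A check that reads such a half-life as shorter would be wrong in the unhelpful direction.

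**Working it through.** **Inputs.** From the documents: the equation, the three dosing patterns, weekly samples, six participants, follow-up to week 6 or 8, and the within-subject CV of 0.20 in the sample-size paragraph. Assumed, because the documents are silent: the true half-life (17 days as illustration, with 28, 34 and 35 as longer cases), linear first-order loss, instantaneous input, pre-dose samples, and the error scale of the fit. The plan states no figure to reproduce here.

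**1. Dose amount.** Multiplying the data by 0.33, 1 or 10 leaves the fitted half-life at 17.0 days, because Css takes up the factor.

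**2. Dose timing.** With doses at times t_j, C(t) = A × Σ exp(−k(t − t_j)). For daily dosing and a pre-dose sample this sums to A·e^(−k)(1 − e^(−kt))/(1 − e^(−k)), which is exactly the interim form. For 33% dosing it is not. With k = ln 2/17 = 0.0408 and A = 1:

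- Day 7, doses on days 0, 3 and 6: e^(−7k) + e^(−4k) + e^(−k) = 2.56. One third of the daily-dosing value is 5.97/3 = 1.99, so the ratio is 1.29. In dose counts this is 3 doses against 7/3 = 2.33.
- Day 14: 5 doses against 14/3 = 4.67; ratio of levels 1.05.
- Day 42, last dose on day 39: 6.30 against 6.57; ratio 0.96.

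The first point sits high and the week-6 point low. The curve therefore seems to flatten sooner, and fitted k is too large.

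**3. Fitted half-life for a true 17 days** (noise-free, pre-dose, instantaneous input):

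| Fit | Week | 33% | 67% | 100% |
|---|---|---|---|---|
| Unweighted | 6 | 12.9 | 15.1 | 17.0 |
| Unweighted | 8 | 15.2 | 16.4 | 17.0 |
| Log scale | 6 | 11.2 | 14.7 | 17.0 |
| Log scale | 8 | 13.0 | 15.6 | 17.0 |

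On 33% the half-life is short by 24% (1 − 12.9/17) at week 6 and 11% (1 − 15.2/17) at week 8 unweighted, and by 34% and 24% on the log scale.

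**4. What could be masked on 33% alone.** The true half-life that reads as 17 days is 23 days at week 6 or 19 days at week 8 (unweighted). In the worst variant, a log-scale fit at week 6, it is about 28 days.

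**5. Sensitivity.**

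- Samples just after a dose, week 6, unweighted, true 17 days: 14.5/13.7/15.0 days on 33/67/100%. The gap nearly closes and 67% is lowest.
- A 1-day formation half-life, true 28 days, over both weeks and both error scales: 25.1 to 28.3 days on 33%, and 30.3 to 41.3 days on 67% and 100%. The error now runs upward on two regimens, but the gap between regimens remains.

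**6. Six participants together.** If the block size is six (not stated), two start on each regimen. The geometric mean over regimens, unweighted and pre-dose, reads 14.9 days (week 6) or 16.2 days (week 8) for a true 17, and 28.6 or 32.1 days for a true 34. The ratios are 28.6/14.9 = 1.92 and 32.1/16.2 = 1.98. With the log fit at week 6 the readings are 14.1 and 26.3 days, ratio 1.87.

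**7. The alternative.** Fitting the dose-date sum in step 2 to the same noise-free data returns 17.0 and 34.0 days on all three regimens at both weeks.

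**The case against.** A reader might infer that the note about dose is an error. It is not: it is correct for the dose amount (step 1), and what is missing is a statement about dose dates.

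A reader might also infer that the check can hide a long TAF half-life. The documents do not support that. A true 28 days reads as 16.9 only when 33% dosing, a log-scale fit, week 6, pre-dose sampling and instantaneous input all coincide, and the plan fixes neither the error scale, nor the week, nor the time of sampling relative to dose. The unweighted fit gives 20.3 days at week 6 and 24.9 at week 8, and a 1-day formation half-life largely removes the masking. Nor does the error always run towards a shorter half-life (step 5). The check also uses six people, not one on 33%, and a doubling shows in their average.

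Three further points stand. The plan already limits the check to very large differences. Matched TDF simulations would cancel most of the bias: on one schedule a doubling gives a ratio of 1.85 to 2.0 with week-6 pre-dose samples and an unweighted fit, and 1.71 in the worst variant. And noise exceeds the bias: at CV 0.20 and week 6, the 5th to 95th percentile range of the six-person median is 10.3 to 25.8 days for a true 17 and 17.0 to 148 days for a true 35.

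These points reduce the concern without removing it. Admitting low sensitivity is not the same as disclosing a systematic shift, and the text does not require matched simulations. The shift also survives averaging: pooling six participants with a common k on the log scale (week 6, CV 0.20), a true 17 days has median 14.1 days with the equation as written and 17.2 with dose dates; a true 28 days gives 21.9 against 27.8.

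**Conclusion.** The concern holds as a minor point. The interim equation needs the dosing pattern, the plan does not supply it, and the fitted k therefore depends partly on the assigned regimen. For an assumed 17-day half-life the fitted value on 33% dosing is 11% to 24% short with an unweighted fit and 24% to 34% short on the log scale, given pre-dose samples and instantaneous input. On that regimen alone a moderate rise in half-life, to 19 to 23 days or at most about 28, could pass as 17. A doubling remains visible in the six-participant point estimates, subject to noise. Both the size and the direction of the shift rest on assumptions that the documents leave open: half-life, sampling time, error scale and formation delay. The primary analysis of dose proportionality does not use this k; it uses measured week-12 levels, checked against PK modelling.

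**What to change.** In the interim section:

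- Replace the equation with C(t) = A_i × Σ exp(−k(t − t_j)), summed over the recorded directly observed dose dates t_j, with a participant-specific A_i and one k common to the six participants. Add a formation term if the data call for it.
- Generate the DOT-DBS (TDF) simulations with the same regimens, dose dates and sampling days, and fit them with the same model.
- Keep the note but reword it: the dose amount is not required, the dose dates are.

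The cost is one changed equation and a few lines of code. Directly observed dosing should already supply the dose dates, and no new samples are needed.
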